In literature, when we talk about telemedicine and pharmacists we often refer only to telemonitoring of glycemic values (7). Furthermore, telemedicine is seen as an advantageous tool only for rural and isolated areas, but its potential can also be appreciated in urban areas (8-10). In fact, from its use in the early diagnosis of complications and in the follow-up of diabetic patients it would result not only a reduction in the workload of health facilities that could devote more time to the care of those

patients who require more information than those who only need undergo a screening of the complications, but also a reduction of the costs related to the personnel and the infrastructures necessary to carry out the activities foreseen by the diagnostic therapeutic assistance plans. Moreover, the possibility of being able to undergo the necessary examination at any hour of the day, would certainly improve the adherence of the patients to the planned checks, a rapid identification of the complications and an early start of the necessary treatments.

On the other hand, clinical self-analysis equipment and telecarefertation systems (ecg, ocular fund, etc.) have reached maturity so that they can be used without reserve in the clinical management of patients.

The scenario at the base of the present study in which the contracted community pharmacist assumes the role of case manager of the patient suffering from type 2 diabetes mellitus and the pharmacy becomes the place where to perform the checks foreseen by the individual assistance plan in a flexible way (smart clinic), appears to have not been the subject of previous studies.

3. Study Objectives

Primary Endpoint

The primary objective of the study is the variation - compared to a historical cohort - of the percentage of adherence to PDTA (patients who performed the scheduled checks at 3-6-12 months / total of patients enrolled x 100) in the cohort of patients enrolled in the study and therefore followed by a case manager identified in the community pharmacist with the opportunity to perform the checks provided in telemedicine and self-analysis, thanks to the exploitation of the “pharmacy of service”.

Secondary Endpoints

The secondary objectives of the study are:

- variation in waiting times for the execution of the examinations envisaged by the PDTA;
- variation in levels of HbA1c, LDL-cholesterol, arterial pressure

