- assessment of the economic impact secondary to the establishment of the figure of the Case Manager and the use of the “pharmacy of service”;
- assessment of the variation in the quality perceived by patients in carrying out this innovative treatment path, compared to the traditional model.

4. Study procedures

The study, whose duration will be 12 months (November 2018 - October 2019), which does not include any cost for the Italian National Health Service and for the same patients participating, is of type:

- observational
- prospective,
- single-center,
- no profit.

The following are the main phases of the research project.

Phase 1: Patient Enrollment (November 2018)

In the first phase, with a total duration of one month, patients are enrolled, presenting the characteristics indicated below, in a number equal to as a result of the detailed calculation in paragraph 8.

Phase 2: Review, database validation and definition of Individual Assistance Plan (December 2018)

In December 2018, the database is validated and the individual assistance plans defined by the general practitioners involved.

Phase 3: Case Management e follow up (December 2018- October 2019)

In the remaining months the Case Manager follows the patients in carrying out the checks provided by the reference PDTA and the Individual Assistance Plan drawn up by the attending physician.

ECG (performed with an electro cardiograph Microtel BT and reported by the HTN Srl power station), ocular bottom (performed with Nexty non-mydriatic fundus camera and reported by Next Sight Srl) and self-analysis (glycated hemoglobin, lipid profile and microalbuminuria, performed with Farmascreen device of Biochemical Systems International Spa) will be carried out directly in the pharmacy using the above mentioned reporting equipment and platforms. For the services requested that can not be carried out at the pharmacy, the pharmacist proceeds with the prescription from the General Practitioner, the booking of the exam by means of the CUP service and the execution of a telephone reminder service that reminds the patient when 'exam. Each performance is reported to the attending physician by sending the report in electronic format.

5. Study estimated duration

The study will last 12 months, from November 2018 to October 2019.

6. Inclusion and exclusion criteria

Recruitable patients:

- age > 18 years,
- patients with type 2 diabetes mellitus;
- able to express consent to the study

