- regularly attending the trial site (Pharmacy [name] [name])

7. Case Report Form (CRF)

Electronic data collection forms are provided (Case Report Form - CRF) necessary for the collection of clinical information of the patient, together with those of an organizational and management nature.

The detail of the information to be collected is defined in the data collection forms.

For the purpose of a homogeneous data collection, for each patient belonging to the target population, a form is provided, whose structure generally foresees the following macro-areas:

- general information on the patient (ID, gender, age, etc.);
- near and remote pathological anamnesis
- vital parameters and input blood analysis

- examinations and procedures required for follow-up
- results and reports of the controls carried out during the follow up;
- perceived quality questionnaire.

8. Sample size and statistical analysis

Starting from the percentage of adherence to all the controls envisaged by the PDTA in a historical cohort described in the work carried out by the Emilia Romagna Region on the prevalent cases of 2015 (11) equal to 4%, a simple size of 20 patients is necessary to demonstrate the effectiveness of our intervention in order to increase the percentage of adhesion to 29%, with an error α of 0.05 and a statistical power (error $1-\beta$) of 95%. To avoid any dropouts or consensus withdrawals, the necessary sample was doubled to 40 patients.

The formula used to calculate the simple size is as follows:

$$N = \frac{p_0 q_0 \left\{ z_{1-\alpha/2} + z_{1-\beta} \sqrt{\frac{p_1 q_1}{p_0 q_0}} \right\}^2}{(p_1 - p_0)^2}$$
$$q_0 = 1 - p_0$$
$$q_1 = 1 - p_1$$
$$N = \frac{0.04 * 0.96 \left\{ 1.96 + 1.64 \sqrt{\frac{0.29*0.71}{0.04*0.96}} \right\}^2}{(0.29 - 0.04)^2}$$
$$N = 20$$

p_0 = proportion (incidence) of population
 p_1 = proportion (incidence) of study group
 N = sample size for study group
 α = probability of type I error (usually 0.05)
 β = probability of type II error (usually 0.2)
 z = critical Z value for a given α or β

The statistical analysis of the collected data will be developed through descriptive analysis.

The economic evaluation will be performed by comparing the costs incurred in the traditional path and the costs deriving from the application of the model under study, calculated with reference to the regional rate where appropriate.

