The assessment of the perceived quality will be carried out through a short anonymous questionnaire administered at the end of the study to all the subjects enrolled.

All categorical variables measured in this study will be expressed as an absolute number and a percentage. Continuous variables will be expressed as mean and standard deviation or median and interquartile range [IQR], depending on the normal or non-data distribution.

The differences will be analyzed by chi-square tests, t-tests for unpaired data or by Mann-Whitney U tests, depending on the nature of the variable.

Any difference with a $p < 0.05$ will be considered statistically significant.

9. Results expected by the study

The problem of the poor adherence to the controls envisaged by the PDTA diabetes is a well-highlighted phenomenon but to which it is difficult to find a solution that gives tangible results in the short and long term, as can be seen from what can be found in the literature. The main causes of non-adherence reported in the aforementioned study (11) emerged from the focus groups conducted with patients and operators are the lack of a reference figure present continuously over time, motivating and able to give answers on several fronts (eg a nurses in group medicine and / or in the homes of health) and the difficulty of reconciling the management of the disease with the rhythms of life.

The present study by overcoming these critical issues, thanks to the use of the unexpressed potential of the “pharmacy of service” (remote execution of the services provided by the PDTA) and of the pharmacist, as a case manager, alongside the basic and specialist medicine, it will improve the current quality of care for type 2 diabetic patients (+ 25% adherence to the PDTA), with a view to sustainability.

10. Ethical Considerations

To protect privacy, the patients of the group described above will be identified only by means of progressive numerical codes (ID).

The data will be treated with confidentiality and confidentiality and disclosed only in aggregate and anonymous form.

The protection of subjects will be guaranteed as recommended in the Oviedo Convention (Convention for the Protection of Human Rights and the dignity of the human being in relation to the application of biology and medicine: Convention on Human Rights and Biomedicine - 4 April

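### No comparator or time point is given for the change in HbA1c, LDL-cholesterol and blood pressure, and the only tests named for continuous variables do not suit the likely before/after comparison

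*Combined protocol and SAP*

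**What the plan says.** The clinical secondary endpoint in section 3 reads, in full, "variation in levels of HbA1c, LDL-cholesterol, arterial pressure". No comparator and no time point follow.

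Three of the other four endpoints do name an outside comparator. Adherence, the primary endpoint, is "compared to a historical cohort" (section 3). Perceived quality is "compared to the traditional model" (section 3). Costs are set against those of the traditional path (section 8). The fourth, waiting times, names none.

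On data sources, section 4 (Phase 3) has the pharmacy perform "self-analysis (glycated hemoglobin, lipid profile and microalbuminuria" during follow-up. Section 7 says that "for each patient belonging to the target population, a form is provided". That form covers "vital parameters and input blood analysis" and also the results of the follow-up checks. For the specific variables, "The detail of the information to be collected is defined in the data collection forms". Section 10 identifies patients by a numeric code.

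On analysis, section 8 first calls it descriptive. It then adds "The differences will be analyzed by chi-square tests, t-tests for unpaired data or by Mann-Whitney U tests", with the choice depending on the type of variable, and treats any difference with p < 0.05 as significant. No paired or repeated-measures method appears in the document.

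**The concern.** A variation has to be measured against something. If that is the patient's own entry value, the two sets of measurements come from the same people and are usually positively correlated. The unpaired t-test and the Mann-Whitney U test assume independent groups. They would ignore the correlation and use too large a standard error, so a real change in HbA1c, LDL-cholesterol or blood pressure could be reported as non-significant in a study of at most about 40 patients.

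If the comparator is instead an outside group, unpaired tests could be suitable, but the plan then lacks the source and values for that group. Either way section 8 is incomplete for this endpoint, and a reader cannot tell which test is right.

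**Working it through.** **1. The plan's own figure.** Section 8 gives a sample size only for adherence (4% vs 29%). With its formula: p₀q₀ = 0.04 × 0.96 = 0.0384; p₁q₁ = 0.29 × 0.71 = 0.2059; √(0.2059/0.0384) = 2.316; N = 0.0384 × (1.96 + 1.64 × 2.316)² / 0.25² = 20.4. The stated 20 reproduces (21 if rounded up). It was doubled to 40 to cover dropouts and withdrawals. Nothing below changes it.

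**2. What could the comparator be?**

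| Endpoint | Comparator named | Outside value given |
|---|---|---|
| Adherence (primary) | Historical cohort | 4% |
| Costs | Traditional path | Regional rate, where appropriate |
| Perceived quality | Traditional model | None |
| Waiting times | None | None |
| HbA1c, LDL-cholesterol, blood pressure | None | None |

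The historical cohort is described only by its 4% adherence. The only HbA1c, lipid and vital-sign data described are entry and follow-up results on one form per patient, so they can be linked. Before/after is therefore the reading the data support, although the plan does not state it.

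**3. Effect of an unpaired test on paired data.** With n pairs, SD σ at both times and correlation r:

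- standard error assumed by the unpaired test: σ√(2/n)
- true standard error of the mean change: σ√(2(1−r)/n)
- ratio: 1/√(1−r) = 1.00, 1.20, 1.41 and 1.83 at r = 0, 0.3, 0.5 and 0.7

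**4. Power.** The documents give no SD, correlation or expected change for these variables. The following are assumptions: bivariate normal data, equal SDs, two-sided 0.05, a true change of 0.4 SD, and r = 0.3 to 0.7. Section 8 requires 20 patients and enrols 40, so 40 complete pairs is the best case and 20 is shown as well.

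Paired power comes from the noncentral t distribution with noncentrality 0.4√n/√(2(1−r)). For example, with n = 40 and r = 0.5 this is 0.4 × 6.325/1 = 2.53 against a critical value of 2.02 on 39 df, which gives 69%. Unpaired power on the same correlated data comes from simulation.

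| r | 40 pairs: unpaired | 40 pairs: paired | 20 pairs: unpaired | 20 pairs: paired |
|---|---|---|---|---|
| 0.3 | 41% | 55% | 20% | 30% |
| 0.5 | 39.5% | 69% | 16% | 40% |
| 0.7 | 37% | 89% | 11% | 59% |

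At r = 0 with 40 pairs the paired test costs about 1 point (41.5% vs 42.3%).

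**5. Type I error.** With 40 pairs, the unpaired t-test's true error is about 2.0%, 0.65% and 0.06% at r = 0.3, 0.5 and 0.7, against a nominal 5%. The error is in the conservative direction.

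**6. Rank tests.** With 40 pairs and a 0.4 SD change, Mann-Whitney gives 38.5%, 37.0% and 34.8%, and Wilcoxon signed-rank gives 53.0%, 67.6% and 87.9%. The pattern is the same.

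**The case against.** The strongest reply is that section 8 never assigns an unpaired test to these three variables. Its sentence is generic, and the same section calls the analysis descriptive. This stands in part: a reader might infer that the plan prescribes the wrong test for HbA1c, LDL-cholesterol and blood pressure, and the text does not say that. However, the descriptive label does not remove the tests and the p < 0.05 rule that follow it, and no other test for continuous variables is available in the plan.

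Second, three of the five endpoints use an outside comparator, so one may be meant here too, and unpaired tests could then be correct. This is possible, and it is why before/after must be called an inference. But no outside values for these variables are described.

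Third, a reader might infer that follow-up blood pressure will not be recorded, because no section describes it explicitly. The documents do not support that: section 7 leaves the detail to forms that are not reproduced. It is a reason to check the forms, not evidence of a gap.

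Fourth, the effect is small. Any error is conservative and the endpoint was never powered. With 20 pairs and r of 0.3 or 0.5, even the paired test has only 30% to 40% power for a 0.4 SD change. All of this stands and limits the weight of the point.

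**Conclusion.** The point holds as a minor one about secondary endpoints. It is certain that the comparator and time point for HbA1c, LDL-cholesterol and blood pressure are unstated, that waiting times also lack a comparator, and that no paired method appears. It is conditional that the named tests are a poor fit: this follows if the comparison is before/after, which is likely but inferred.

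Under that reading, the loss for an assumed 0.4 SD change with r between 0.3 and 0.7 is about 14 to 52 percentage points of power with 40 pairs (55 − 41; 89 − 37) and about 10 to 48 with 20 pairs (30 − 20; 59 − 11). If r is near zero there is nothing to gain. These sizes rest wholly on assumed correlations, equal SDs and an assumed effect.

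Two stronger conclusions are not supported. The named tests would not produce spurious significant findings, since with positive correlation they err the other way. Nor does the issue touch the adherence endpoint or its sample size.

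**What to change.** In section 8, keep the existing sentence for comparisons of independent groups and add, for example: *Change from entry to [follow-up time point, to be stated by the sponsor] in HbA1c, LDL-cholesterol and blood pressure is analysed within patient by paired t-test, or by Wilcoxon signed-rank test if the changes are not normally distributed, with a 95% confidence interval. The number of patients with both values is reported.* The time point is the sponsor's choice: section 3 schedules checks at 3, 6 and 12 months but ties none of them to these variables.

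If an outside cohort is meant instead, name its source and its values for the three variables. State the comparator for waiting times as well. Confirm that the data collection forms record each variable at entry and at the chosen time point.

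The cost is a few sentences and a check of the forms, with no new data if both values are already recorded. There are two downsides. Only patients with both values contribute. And, without a concurrent control, a change from entry cannot be separated from regression to the mean or time trends, so it does not by itself show that the service caused it; the report should say so.

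### Section 8 calls the analysis descriptive, then lets any difference with p below 0.05 be declared significant, with no error control for the secondary outcomes

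*Combined protocol and SAP*

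**What the plan says.** The protocol, Section 3, names one primary endpoint: the percentage of patients adherent to the PDTA (checks at 3, 6 and 12 months), compared with a historical cohort. The secondary outcomes are waiting times, "variation in levels of HbA1c, LDL-cholesterol, arterial pressure", economic impact and perceived quality.

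Section 8 sizes the study on adherence alone. It starts from a historical figure of 4% and plans the intervention "in order to increase the percentage of adhesion to 29"%, with alpha 0.05 and 95% power. This gives 20 patients, and "the necessary sample was doubled to 40 patients".

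The analysis text in the same section opens with "The statistical analysis of the collected data will be developed through descriptive analysis". After the rules for summarising variables it continues: "The differences will be analyzed by chi-square tests, t-tests for unpaired data or by Mann-Whitney U tests", according to the type of variable. It closes with the rule that any difference with p below 0.05 "will be considered statistically significant". Section 8 contains no order of testing, no adjustment for multiple tests and no statement that secondary results are exploratory.

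**The concern.** The two parts of the analysis text pull in different directions. A descriptive analysis makes no significance claims. The closing rule makes one for every difference that crosses the threshold, whichever outcome it concerns. The analyst cannot tell which secondary outcomes are meant to support inference.

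The threshold of 0.05 was chosen as the error rate of the adherence comparison. Applied to every outcome, it limits the error of each test but not of the set. Adherence could fail to improve, and a chance finding in waiting time or LDL-cholesterol could still be reported as significant under the plan's own rule. Because the sample size is justified by the aim of demonstrating effectiveness, such a result could easily be read as support for the model.

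**Working it through.** **1. The plan's own figure.** Inputs from Section 8: p0 = 0.04, p1 = 0.29, z = 1.96 (two-sided 0.05) and z = 1.64 (95% power).

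- √(p1q1/p0q0) = √(0.2059/0.0384) = 2.316
- N = 0.0384 × (1.96 + 1.64 × 2.316)² / 0.25² = 20.37

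The stated 20 is reproduced, apart from rounding up to 21. The calculation involves one proportion against one fixed value, so alpha 0.05 belongs to that comparison and to no other.

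**2. Number of comparisons.** The documents do not give it. These readings of Section 3 are assumptions:

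- Five: adherence, waiting times, HbA1c, LDL-cholesterol and arterial pressure. Cost is left out because no test is named for it. Perceived quality is left out because one questionnaire at the end of the study supplies no comparator data.
- Seven: each named outcome once, including cost and quality.
- Eight: as seven, with systolic and diastolic pressure tested separately.
- Nine: as seven, with adherence tested at each of three time points.
- Ten: both splits.

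**3. Chance of at least one p below 0.05, no true effects, independent tests.** Two-sided, either direction: 1 − 0.95^k. Falsely favourable only: 1 − 0.975^k, since half of each two-sided error lies on the favourable side.

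| k | Either direction | Favourable only |
|---|---|---|
| 5 | 22.6% | 11.9% |
| 7 | 30.2% | 16.2% |
| 8 | 33.7% | 18.3% |
| 10 | 40.1% | 22.4% |

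If the primary endpoint is set aside, the five-test reading leaves four secondary tests: 1 − 0.95^4 = 18.5% in either direction and 1 − 0.975^4 = 9.6% favourable. With pressure split and cost and quality tested, there are seven secondary tests, and the row for seven applies.

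**4. Effect of correlation.** The outcomes come from the same patients, so independence is a high-side assumption. Simulation of two-sided z-tests with a common correlation (400,000 replicates) gives, in either direction:

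| k | Correlation 0.3 | Correlation 0.5 | Correlation 0.8 |
|---|---|---|---|
| 5 | 21% | 18% | 13% |
| 8 | 30% | 25% | 16% |
| 10 | 35% | 29% | 17% |

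The limit with full correlation is 5%. The documents give no correlations, so these values only show the range.

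**5. The primary endpoint.** Tested once, its error rate stays at 0.05 whatever is done with the secondary outcomes. If it were tested separately at 3, 6 and 12 months as three independent tests, the figure would be 1 − 0.95³ = 14.3%, again lower with correlation.

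**The case against.** The strongest reply is that this is a small, single-centre, non-profit study that calls itself observational. It designates one primary endpoint, labels the rest secondary, and frames its expected result in Section 9 on adherence (+25%). It claims no overall error rate, and nothing in it says that a secondary result may stand in for a failed primary one. The word descriptive may be loose wording for summaries followed by tests. Formal adjustment of secondary outcomes would be more than such a study needs.

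Much of this stands, and it rules out several stronger readings:

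- A reader might infer that the plan commits to at least eight comparisons and so to a one-in-three chance of a false positive. It does not. Seven outcomes are named, only five are clearly testable, and one in three also requires independent tests and no true effects.
- A reader might infer that the alpha stated for the primary endpoint is broken. It is not, provided that endpoint is tested once.
- A reader might take the two-sided figures as the chance of a false benefit. That chance is about half as large.
- A reader might conclude that the two statements are strictly irreconcilable. A lenient reading can hold both, although the text does not say so.

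The closing rule itself does not fall. It is an explicit instruction covering any difference, not a missing detail, and neither the secondary label nor the descriptive sentence limits it. An exploratory label would meet the concern without formal adjustment, but the plan does not have one.

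**Conclusion.** The point holds in a limited form. Section 8 describes the analysis as descriptive and then permits a significance claim for every outcome, while alpha and the sample size concern adherence alone. The primary test is not affected if it is done once. The weakness lies in what may be claimed from waiting times, HbA1c, LDL-cholesterol and arterial pressure, and from cost or perceived quality if these are tested.

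The size depends on a count that the documents do not give. For five to ten independent tests with no true effects, the chance of at least one p below 0.05 is about 23% to 40%. Positive correlation reduces it, to about 25% for eight tests at 0.5. For falsely favourable results the range is about 12% to 22% under independence. The need to clarify the text does not depend on any of these counts. This is an inexpensive improvement to the rule for claims, not a flaw in the primary comparison.

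**What to change.** Three changes to the analysis text of Section 8:

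1. Replace the closing sentence on significance with, for example: *The only confirmatory test is one overall test of the primary adherence endpoint, at two-sided alpha 0.05. Secondary outcomes are exploratory; they are reported as estimates with 95% confidence intervals and are not declared significant.*
2. Limit the sentence on descriptive analysis to the secondary outcomes.
3. Amend the sentence on chi-square, unpaired t and Mann-Whitney tests so that any p-value for a secondary outcome is labelled nominal and exploratory. Without this change the section would still prescribe tests for outcomes that it now calls descriptive: the primary endpoint is a proportion, so the t and Mann-Whitney tests can only serve secondary outcomes.

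A Bonferroni threshold is the alternative (0.05/8 = 0.00625 for eight tests), but it would be severe with 40 patients, and estimation suits the design better. The change needs no further patients or data and takes no power from the primary test. The downside is that secondary results can no longer be headlined as significant.
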